10.4 Handling of Multiplicity

The statistical comparisons for the primary efficacy variable and the ranked secondary variables will be carried out in the hierarchical order. This means that statistically

significant results (P value ≤ 0.05) for the comparison in the higher rank (primary, then ranked secondary variables) are necessary to initiate the testing of the next comparison in the lower rank. Since a step-down procedure is used, each comparison will be tested at a significance level of 0.05 and overall alpha level of 0.05 will be preserved.

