Safety criteria:	Physical examinations, vital signs, 12 lead electrocardiogram (ECG), laboratory testing, adverse events, local tolerability	
Statistical methods:	
Co-primary analysis: The achievement of PASI 90 and sPGA of clear or almost clear at Week 16 are the co-primary endpoints and are binary variables with values of 0 or 1. The difference in proportion responding between the BI 655066 arm and placebo arm will be estimated and tested using the Cochran-Mantel-Haenszel risk difference estimate stratified by the randomisation factors of weight (≤ 100 kg versus >100 kg) and prior exposure to TNF antagonists (0 versus ≥ 1) with weights proposed by Greenland & Robins.
 
Secondary analysis: The same methods for the primary analyses will be used to analyse all secondary endpoints since they are all binary endpoints.
 
All hypotheses will be tested in a hierarchical order using two-sided tests with a type I error of 0.05.
	

FLOW CHART 1

Trial Protocol

Page 7 of 101

Proprietary confidential information © 2016 Boehringer Ingelheim International GmbH or one or more of its affiliated companies

Trial Period	Screening												Treatment												Follow-up			
	1	2	3	4	5	6	7	8	9	10	11	12	13	14	15	16	17	18	19	20	21	EOT	Follow-up #1 ¹²	Follow-up #2 (EOO)				
Visit																												
Week																												
Day	-42 to -7	1	28	56	84	112	140	168	196	224	252	280	308	336	364	406	448	490	532	574	616	658	694	728	104	EOT+ 16wks		
Visit window (days)	N/A	±3	±7	±3	±7	±3	±7	±7	±7	±7	±7	±7	±7	±7	±7	±7	±7	±7	±7	±7	±7	±7	±7	±7	±7	±7		
IJC/SJC, DAS ¹⁸	X					X																				X		
sPGA assessment of relapse ²²																												
Termination of trial drug ¹⁵																												
Trial completion																												
Open label extension ⁶																										X ⁶		
Vital Status ²⁰																										X		

Flow Chart 1 Footnotes

1. Pregnancy Testing: X_s =serum testing; Xu= onsite urine testing; Serum pregnancy is done at screening and as a reflex when urine testing is positive.
2. Voluntary DNA banking sample will be stored after informed consent is given. This may be a separate informed consent or part of the main informed consent in accordance with local ethical and regulatory requirements. Refer to Section 5.5

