7.2 NULL AND ALTERNATIVE HYPOTHESES

The primary hypotheses are that BI 655066 is different than placebo in achieving $\geq 90\%$ reduction from baseline in the Psoriasis Area and Severity Index score (PASI 90) and sPGA of 0 or 1 at Week 16 in participants with moderate to severe chronic plaque psoriasis. For the primary analyses, this study has 2 treatment arms:

Arm 1 – Patients randomised at visit 2 to receive 150 mg of BI 655066
Arm 2 – Patients randomised at visit 2 to receive placebo

For Part B of the trial, patients randomised to receive BI 655066 at visit 2 and have an sPGA response of 0 or 1 at Week 28 will be re-randomised to one of the following treatment arms:

Arm A – Patients re-randomised to continue to receive BI 655066 during Part B
Arm B – Patients re-randomised to receive placebo during Part B

The following null hypotheses will be tested in a hierarchical order using two-sided tests with a type I error of 0.05. The two co-primary endpoints need to be significant simultaneously, therefore no alpha adjustment is necessary.

1. BI 150 mg (Arm 1) is not different from placebo (Arm 2) with respect to PASI 90 or sPGA 0 or 1 response at Week 16
2. BI 150 mg (Arm 1) is not different from placebo (Arm 2) with respect to PASI 75 response at Week 16
3. BI 150 mg (Arm 1) is not different from placebo (Arm 2) with respect to PASI 100 response at Week 16
4. BI 150 mg (Arm 1) is not different from placebo (Arm 2) with respect to achieving an sPGA score of clear (0) at Week 16
5. BI 150 mg (Arm 1) is not different from placebo (Arm 2) with respect to achieving a DLQI score of 0 or 1 at Week 16.

For the re-randomized patients, the following null hypothesis will be performed with a type I error of 0.05.

- Arm A (patients re-randomised to BI 655066) is not different from Arm B (patients re-randomised to placebo) with respect to sPGA 0 or 1 response at Week 52.

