Description of change		Added a paragraph for TB testing: “Patients will be tested for TB (Quantiferon or PPD) at Screening, Week 52 and EOO. Patients who test positive and are at low risk of TB reactivation, per local guidelines and investigator judgment, do not need to be treated with prophylactic anti-tuberculosis medication and can be entered or continue in the trial”.
Rational for change		New screening procedure and information on

Proprietary confidential information © 2016 Boehringer Ingelheim International GmbH or one or more of its affiliated companies

	treatment upon testing positive.
Section to be changed	Section 6.2.1, Screening period
Description of change	The maximum of 2 visits that a patient may need for screening was deleted
Rationale for change	Patients may require more than 2 visits to the clinic during screening
Section to be changed	Section 6.2.3, Follow-up Period and Trial Completion
Description of change	1. Vital status- patients must follow their current flow chart for EOO 2. Removed criteria for missing one dose for eligibility for OLE study 3. Patients discontinuing treatment early should continue in the study
Rationale for change	1. Clarification for relapse and re-treated patients following FC#2 and FC#3 2. Clarification 3. Added for Clarification
Section for change	Section 7.2 Null and Alternative Hypothesis
Description of change	Separated out re-randomized hypothesis from hypotheses tested on all randomized patients
Rationale for change	The re-randomized portion of the trial can be treated as a separate study and thus tested with its own alpha = 0.05.
Section for change	Section 7.3- Planned Analysis
Description of change	1. Clarifying the definition of analysis sets 2. deleted wording that IPV's would be provided in TSAP and added verbiage about IPVs and PPS sensitivity analyses 3. Added "The hypothesis tests as described in Section 7.2 will be repeated on the PPS or RRS-PPS populations, as appropriate".
Rationale for change	In response to questions from Health Authorities.
Section for change	Section 7.4-Interim analysis
Description of change	Removal of DMC information

Proprietary confidential information © 2016 Boehringer Ingelheim International GmbH or one or more of its affiliated companies

Rationale for change	Redundant as included in DMC section
Section for change	Section 7.5 Handling of Missing data

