The mean and median will be rounded for presentation to 1 decimal more than the data entered into the database. The standard deviation will be rounded to 2 decimal places more than the data entered into the database. The minimum and maximum values will be presented as entered into the database.

Probabilities will be rounded to 3 decimal places before assignment of statistical significance and will be presented in rounded format. Probabilities that round to zero or are reported by SAS as zero will be presented as "< 0.001." Probabilities that round to 1 or are reported by SAS as 1 will be presented as "> 0.999."

7.0 Demographics, Baseline Characteristics, Medical History, and Previous/Concomitant Medications

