10.2.2 Primary Efficacy Analysis in Part B

Achievement of an sPGA of clear or almost clear (0 or 1) at Week 52 is the primary endpoint for Part B under re-randomization. This endpoint will be tested independently with a type I error rate of 0.05, for the ITT_B_R Population. A sensitivity analysis will also be performed on the same endpoint for the PP_B_R Population.

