10.3.1.2 Ranked Secondary Efficacy Analysis in Part B

The ranked secondary endpoint for Part B is the achievement of sPGA of clear or almost clear (0 or 1) at Week 104.

This ranked secondary endpoint will be analyzed for the ITT_B_R Population. The same methods as discussed for the primary analyses will be used.

The null hypotheses below will be tested in a hierarchical order in the final analysis only, using two-sided tests with a type I error of 0.05 only if the null hypothesis for the primary endpoint in Part B has been rejected:

- Continuation of risankizumab is not different from switching to placebo with respect to sPGA of clear or almost clear (0 or 1) response at Week 104.

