14.0 Summary of Changes

14.1 Summary of Changes Between the Latest Version of Protocol and the Current SAP

- Defined analysis populations (including the Per-protocol population) in detail.
- Clarified independent null hypothesis test hierarchy in the ITT Population in Part B consisting re-randomized subjects.
- Added additional ranked secondary endpoint to the ITT Population in Part B consisting re-randomized subjects: achievement of sPGA of clear or almost clear (0 or 1) at Week 104.
- Pre-specified Areas of Safety Interest.

14.2 Summary of Changes Between the Previous Version and the Current Version of the SAP

Updated Table 25, Table 27, and Table 28 based on Integrated Summary of Safety SAP.

Updated the end day for inclusion concomitant medications, based on Integrated Summary of Safety SAP.

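### SAP 10.4 claims an overall alpha of 0.05, but Parts A and B are two ungated chains, so 0.05 holds only within each part (nominal trial-wide maximum 9.75%).

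*SAP*

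**What the plan says.** SAP 10.4 (Handling of Multiplicity) presents one ordering, primary first and ranked secondaries after it. It infers from the step-down that "each comparison will be tested at a significance level of 0.05 and overall alpha level of 0.05 will be preserved". It names no study part.

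The testing rules are set out in the sections before it:

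- **Part A (SAP 10.2.1, 10.3.1.1).** PASI 90 and sPGA 0 or 1 at Week 16 are co-primary. Each is tested two-sided at 0.05 and both must succeed. PASI 75, PASI 100, sPGA 0 and DLQI 0 or 1 follow in order, gated only on the Part A co-primaries.
- **Part B (SAP 10.2.2, 10.3.1.2).** For sPGA 0 or 1 at Week 52: "This endpoint will be tested independently with a type I error rate of 0.05, for the ITT_B_R Population". Week 104 is tested "only if the null hypothesis for the primary endpoint in Part B has been rejected".

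The separation is intended. Protocol 7.2 lists the Part B test apart from the five-step Part A order: "For the re-randomized patients, the following null hypothesis will be performed with a type I error of 0.05". The Amendment 1 rationale in Protocol 11 reads "The re-randomized portion of the trial can be treated as a separate study and thus tested with its own alpha = 0.05". SAP 14.1 records the change as "Clarified independent null hypothesis test hierarchy in the ITT Population in Part B consisting re-randomized subjects". SAP 4.1 gives each randomised phase its own primary objective.

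Two other statements bear on the point. The statistical methods in the protocol synopsis say "All hypotheses will be tested in a hierarchical order using two-sided tests with a type I error of 0.05", with no exception for Part B. SAP 6.0 says "Probabilities will be rounded to 3 decimal places before assignment of statistical significance", and SAP 10.1 applies the same rounding to the 0.05 level.

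**The concern.** A step-down protects 0.05 along one chain. It gives no joint protection to two chains that each begin at 0.05 with nothing linking them. The reason given in 10.4 therefore does not support the overall level it states. A reader of that section would conclude that the chance of any false rejection among the trial's confirmatory tests is at most 5%. That is true of each part alone and untrue of the two together.

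The loose wording also leaves gates unclear. Read literally, 10.4 could make the Part A ranked endpoints wait for every primary, including Week 52, whereas SAP 10.3.1.1 does not. The synopsis places Week 52 sPGA last among the key secondaries and puts all hypotheses in one order, so a DLQI failure would block Week 52. Protocol 7.2 and SAP 10.2.2 say it would not.

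**Working it through.** **Inputs.** Two-sided 0.05 per test (SAP 10.2.1, 10.2.2, 10.3.1). Gates as in SAP 10.3.1.1 and 10.3.1.2. Rounding to three decimals (SAP 6.0, 10.1). The documents give no correlation between the co-primaries, so 0, 0.5 and 0.9 are assumed.

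**1. The plan's figure, part by part.** In a fixed sequence, a false rejection requires rejecting the first true null reached, and that null is tested at 0.05. The co-primary step requires both tests to succeed, so its error cannot exceed that of a single true-null test, again 0.05. The maximum is therefore 0.05 in Part A and 0.05 in Part B. The stated 0.05 reproduces within each part.

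**2. Both parts together.** Responders are re-randomised at Week 28, so the Part B test keeps its nominal level given the Part A data. The product rule then applies:

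1 − (1 − 0.05)(1 − 0.05) = 1 − 0.9025 = **0.0975**

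Without independence the bound is 0.05 + 0.05 = 0.10. The stated overall 0.05 does not reproduce. The maximum is reached, for example, when the co-primaries truly work, a ranked Week 16 endpoint is null and Part B is null.

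**3. Every null true.** Part A then errs only if both co-primaries succeed by chance. Let P be that probability, from a bivariate normal. The trial-wide rate is 1 − (1 − P)(0.95).

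| Assumed correlation | P | Trial-wide rate |
|---|---|---|
| 0 | 0.0025 | 0.0524 |
| 0.5 | 0.0093 | 0.0588 |
| 0.9 | 0.0297 | 0.0782 |

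**4. Rounding.** A raw p just under 0.0505 rounds to 0.050 and counts as significant, so each test has size 0.0505. The maximum becomes 1 − 0.9495² = 0.0984, and the all-null rates become 0.0529, 0.0594 and 0.0790. The effect is about 0.1 percentage point.

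**5. Simulation of the maximum case.** Four million draws gave 0.0976 unrounded and 0.0986 with rounding.

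**6. Check on independence.** A simulation of 400,000 trials used 400:100 in Part A and 107:213 in Part B. Response rates were assumed at 50% in Part A and about 75% in Part B, with the unpooled normal-approximation test and no stratification. The correlation between Part A and Part B rejections was 0.0006. The tests themselves ran slightly above nominal, at 5.22% and 5.24%. The combined rate was 10.18%, against 1 − (1 − 0.0522)(1 − 0.0524) = 10.19% from the product rule.

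**The case against.** The strongest reply is that 10.4 follows directly after sections that give each chain its own primary, level and gate, so its rule can be read as applying within each family. On that reading 0.05 is correct, and no gate, test order or sample size changes. That may well be what was meant. But 10.4 does not say so, and it is the SAP section devoted to multiplicity.

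Three qualifications on size have substance:

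- 9.75% is a ceiling. It needs a true null in each part, whereas the protocol assumes 65% vs 5% and 80% vs 5% at Week 16, and 90% vs 75% at Week 52.
- It counts rejections in both directions. With one true null in each part, false findings in favour of the drug amount to 1 − 0.975² = 4.94%. The SAP's alpha is two-sided, however, so 9.75% is the figure comparable with its 0.05.
- It rests on independence and exact test size. The simulated tests ran slightly above 5%. The same caveat applies to every nominal alpha in the SAP, but any figure written into the SAP should be labelled nominal.

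It is also fair that the rounding rule is prespecified, tiny in effect and unrelated to the two chains. It is nevertheless a departure from the 0.05 stated for each test, and removing it is simple.

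**Conclusion.** The concern holds. As written, 10.4 states a property that the testing plan does not have. The familywise error is controlled at 5% within Part A and within Part B (5.05% with rounding), but not across them. The trial-wide nominal two-sided maximum is 9.75% (9.84% with rounding). With all nulls true the rate is 5.2% to 7.8% (5.3% to 7.9% with rounding). These figures assume independent tests in the two parts, tests of exactly the stated size and, for the all-null range, co-primary correlations of 0 to 0.9. The two-family structure is a legitimate, documented choice, and conclusions drawn within either part are not undermined. This should be corrected, but it does not threaten the design.

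**What to change.** Keep the two families as Protocol 7.2 intends, and make three changes before unblinding:

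1. **SAP 10.4.** Replace the closing claim with: *The type I error is controlled at 0.05 within each part (Part A and Part B separately); it is not controlled at 0.05 across both parts (nominal maximum 9.75%, treating the two parts as independent).*
2. **Protocol synopsis.** Align the sentence on hierarchical testing with section 7.2, so that the Part B test is shown as standing outside the Part A order.
3. **SAP 6.0 and 10.1.** Compare unrounded p-values with 0.05 and round only for display.

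The cost is wording in three SAP sections and one protocol sentence, which has to go through an amendment. The trial-level error statement becomes less favourable, and a raw p between 0.0500 and 0.0505 no longer counts as significant.

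A trial-wide 0.05 is not needed for this correction. It would have a price if wanted: splitting alpha 0.025/0.025 would lower Part B power from 90.2% to 83.5% at 102:204, or to 85.4% at the 320 expected re-randomised patients (400 × 0.8).

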10.5 Efficacy Subgroup Analysis

To evaluate the consistency of the efficacy over demographic and other baseline characteristics, summaries and analyses will be performed for selected subgroups for the primary efficacy endpoints in Part A and the primary efficacy endpoint in Part B.

- Age group (< 40 years, ≥ 40 – < 65 years, ≥ 65 years)
- Sex (male, female)
- Race (white, non-white)
- Smoking (current, ex or never)
- BMI (normal: < 25 , over weight: ≥ 25 – < 30 , obese: ≥ 30)
- Region (US, Asia, Other)
- Baseline PASI score (by median)
- Baseline sPGA (3, 4)
- Psoriatic arthritis (yes [diagnosed or suspected], no)
- Ps Therapy History (Phototherapy or Photochemotherapy, TNF Antagonist, Other biologics, Non-biologic systemic therapy, All biologics, Naïve to all)

11.0 Safety Analysis

11.1 General Considerations

Safety analyses will include adverse events, laboratory, local tolerability, ECG, and vital sign measurements. Safety summaries will be provided using the safety population in each period as defined in Section 5.1. Comparison between risankizumab group and placebo group will be performed in the Safety Population in Safety_A1 and Safety_B_R populations. Continuous variables will be analyzed using one-way ANOVA and

categorical variables will be analyzed using Fisher's exact test. For analyses of AEs, only P values ≤ 0.100 when rounded to three digits will be presented.

Missing safety data will not be imputed.

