8.0 Patient Disposition

The number of subjects for each of the following categories will be summarized, for overall and for each treatment group in the ITT_A1 Population:

- Number of subjects randomized
- Number of subjects treated during Part A1
- Number of subjects who completed Part A1
- Number of subjects who discontinued study drug during Part A1
- Number of subjects who prematurely discontinued from Part A1

The number of subjects for each of the following categories will be summarized, for overall and for each treatment group in the ITT_B_R population:

- Number of subjects re-randomized
- Number of subjects treated at Part B
- Number of subjects who completed the Part B
- Number of subjects who received retreatment with risankizumab during Part B at different time points
- Number of subjects who discontinued study drug during Part B
- Number of subjects who prematurely discontinued from the Part B

In addition, the reasons for premature discontinuation will be summarized with frequencies and percentages.

Disposition tables will also be summarized in the ITT_A2, ITT_ARM2, and ITT_B_NR Populations.

In addition to patient disposition, number of screening failures and reasons for screening failure will also be summarized among all screened subjects in a subject screening status table.

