9.0 Study Drug Exposure and Compliance

Summary of study drug exposure will be provided for each treatment arm for all ITT_A1, ITT_A2, ITT_ARM2, ITT_B_R, and ITT_B_NR populations, and the ALL_RZB population. Study drug compliance will be summarized in ITT_A1, ITT_A2, and ITT_B_R populations.

Study drug exposure (days) will be summarized using the sample size, mean, standard deviation, minimum, median and maximum for each treatment part. In addition cumulative exposure of RZB will be also summarized in the ALL_RZB Population. Study drug exposure will be summarized as follows:

Study Drug Exposure (in Days) in Each Period:

Part A1:

For subjects who did not continue into Part A2:

- Date of last injection in Part A1 – Date of first injection in Part A1 + 84.

For subjects who continued into Part A2: the minimum of

- Date of first injection in Part A2 – Date of first injection in Part A1.
- Date of last injection in Part A1 – Date of first injection in Part A1 + 84 days.

Part A2:

For subjects who did not continue into Part B:

- Date of last injection in Part A2 – Date of first injection in Part A2 + 84 days.

For subjects who continued into Part B: the minimum of

- Date of first injection in Part B – Date of first injection in Part A2.
- Date of last injection in Part A2 – Date of first injection in Part A2 + 84 days.

Part B:

For subjects who did not receive retreatment with risankizumab: the minimum of

- Date of last injection in Part B – Date of first injection in Part B + 84 days.
- Cutoff date of 01 September 2017 – Date of first injection in Part B (only for the primary analysis after the last patient either has completed Week 52 visit or discontinues from the study)

For subjects who received retreatment with risankizumab: the minimum of

- Date of first injection of retreatment – Date of first injection in Part B.
- Date of last injection in Part B – Date of first injection in Part B + 84 days.
- Cutoff date (01 September 2017) – Date of first injection in Part B (only for the primary analysis after the last patient either has completed Week 52 visit or discontinues from the study)

ALL_RZB:

For subjects who were re-randomized to placebo in Part B and received retreatment with risankizumab: the minimum of

- Date of last injection of risankizumab in Part A – Date of first injection of risankizumab + 84 days + Date of last retreatment of risankizumab – Date of first retreatment of risankizumab + 84 days.

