For subjects who do not receive retreatment with risankizumab, TEAEs are defined as any event with an onset after the first dose of study drug in Part B and no more than 105 days after the last dose of study drug in Part B.

For subjects who receive retreatment with risankizumab, TEAEs are defined as any event with an onset after the first dose of study drug in Part B and before the first dose of retreatment with risankizumab.

TEAEs of Safety_B_PBO_RT and Safety_B_RZB_RT:

TEAEs are defined as any event with an onset that is after the first dose of retreatment and no more than 105 days after the last dose of study drug.

TEAE of ALL_RZB:

TEAEs are defined as any event with an onset after the first dose of risankizumab through 105 days after the last dose of risankizumab, except for AEs with an onset during protocol-designed treatment gaps (i.e., placebo period) that was more than 105 days from the last dose of the previous risankizumab treatment and before the first dose of retreatment.

Summary tables will be presented as follows:

1. Adverse Event Overview

The number and percentage of subjects experiencing treatment-emergent adverse events will be summarized for the following adverse event categories:

- Any AE
- Any AE that was assessed as related to study drug by the investigator
- Any severe AE
- Any serious AE (SAE)
- Any serious AE that was assessed as related to study drug by the investigator
- Any AE leading to discontinuation of study drug
- Any AE leading to death
- Any deaths
- Areas of Safety Interest

2. Adverse Events by System Organ Class and Preferred Term

TEAEs will be summarized and presented using primary Medical Dictionary for Regulatory Activities (MedDRA) system organ classes (SOCs) and preferred terms (PTs). The SOCs will be presented in alphabetical order, and the PTs will be presented in alphabetical order within each SOC.

Subjects reporting more than one adverse event for a given MedDRA preferred term will be counted only once for that term (most severe incident for the severity tables and most related incident for the relationship tables). Subjects reporting

more than one type of adverse event within a SOC will be counted only once for that SOC. Subjects reporting more than one type of adverse event will be counted only once in the overall total.

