ASI Grouping	Categories (ASI)	Search Criteria	Terms to Display	Include in AE Overview (Y/N)
Serious infections, TB, fungal and opportunistic infections (including herpes zoster) (continued)	Fungal infections	Fungal infections CMQ (code 80000063)	PTs	N
	Herpes Zoster	Herpes zoster CMQ (code 80000175)	PTs	N
Malignancies	All possible malignancies	Narrow – Malignancies (SMQ 20000090)	PTs	N
	Malignant Tumours	Narrow – Malignant tumours (SMQ 20000194)	PTs	Y
	Non-melanoma skin cancer (NMSC)	Broad – Skin malignant tumours (SMQ 20000204) excluding terms identified by the Melanoma CMQ (code 80000119)	PTs	N
	Malignant Tumours excluding NMSC	'Malignant Tumours excluding NMSC' is identified by the 'Malignant Tumours' search excluding terms identified by the 'Non-melanoma skin cancer (NMSC)' search.	PTs	Y

Table 23. Areas of Safety Interest (Continued)

ASI Grouping	Categories (ASI)	Search Criteria	Terms to Display	Include in AE Overview (Y/N)
Hypersensitivity Reaction	Hypersensitivity	Narrow – Hypersensitivity (SMQ 20000214)	PTs	Y – serious events only
	Anaphylactic Reaction	Narrow – Anaphylactic reaction (SMQ 20000021)	PTs	N
Hepatic Events	Hepatic Events	Broad – Hepatic failure, fibrosis and cirrhosis and other liver damage-related conditions (SMQ 20000013) Broad – Hepatitis, non-infectious (SMQ 20000010) Broad – Cholestasis and jaundice of hepatic origin (SMQ 20000009) Broad – Liver related investigations, signs and symptoms (SMQ 20000008) Narrow – Liver-related coagulation and bleeding disturbances (SMQ 20000015)	PTs	N

Adverse Event per 100 Patient-Years of Exposure

Adverse events occurring during the entire study will be presented by event rate per 100 patient-years. These will be presented for any TEAEs, serious adverse events, and Areas of Special Interest.

AEs per 100 patient-years of exposure is defined as the number of AEs divided by the total exposure in 100 patient-years. Note that one event per preferred term per day per subject will be counted in the calculation of the number of AEs (i.e., a preferred term will not be counted twice on the same day for the same subject). See the calculation method below.

$$100 \times \frac{\text{Number of TEAEs}}{\text{Total Patient Years}}$$

where total patient years is defined as the sum of the study drug exposure (defined as date of last dose – date of first dose + 105 days (5 half-lives)) of all subjects normalized by 365.25, and rounded to one decimal place.

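### Part B adverse-event percentages are compared by Fisher's exact test although counting stops at retreatment, so the arms are observed for different times and no AE rate in the SAP matches that window

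*SAP*

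**What the plan says.** SAP 11.1 names two populations for the between-arm safety comparison: "Comparison between risankizumab group and placebo group will be performed in the Safety Population in Safety_A1 and Safety_B_R populations". It adds that "categorical variables will be analyzed using Fisher's exact test", and that AE p-values are shown when they are 0.100 or less.

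SAP 11.2.1 sets the counting window for Safety_B_R. For a retreated patient an event counts if it has "an onset after the first dose of study drug in Part B and before the first dose of retreatment with risankizumab". For everyone else the window runs to 105 days after the last Part B dose. The AE tables count patients.

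Three other places bear on follow-up time:

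- **Disposition (SAP 8.0)** reports by arm the "Number of subjects who received retreatment with risankizumab during Part B at different time points".
- **Part B exposure (SAP 9.0)** is cut at retreatment but is also capped at "Date of last injection in Part B – Date of first injection in Part B + 84 days". At the primary analysis it is further limited by "Cutoff date of 01 September 2017 – Date of first injection in Part B". It is not named as the denominator of any AE rate.
- **AE rates (SAP 11.2.1)** have a different scope: "Adverse events occurring during the entire study will be presented by event rate per 100 patient-years". They count repeat events, and the denominator is last dose minus first dose plus 105 days, with no cut at retreatment.

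Protocol 7.3.4 describes safety as descriptive, with no hypothesis tests. SAP 14.1 does not list safety testing as a change.

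**The concern.** Fisher's exact test on the proportion with at least one event compares like with like only if both arms have the same opportunity to show an event. Here the opportunity ends at relapse. Relapse should be more frequent on placebo, because that difference is what Part B is powered to show (Protocol 7.7). The test therefore mixes event risk with length of observation.

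Part B is the only randomised comparison of risankizumab with placebo after Week 16. For common events other than worsening psoriasis, the longer-observed arm, continued risankizumab, will tend to show the higher percentage even if the drug has no effect on the event. *Any AE* is pulled the other way. Protocol 5.3.7 asks for worsening of the underlying disease to be recorded as an AE, and such events fall mainly on placebo. A comparison whose sign depends on how relapse is coded is hard to interpret in either direction.

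**Working it through.** **1. The plan's own figure.** Protocol 7.7 assumes 90% vs 75% response at Week 52, 1:2 allocation, two-sided 0.05 and 90% power. The pooled proportion is (0.90 + 2 × 0.75)/3 = 0.80.

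n(risankizumab) = [1.96√(0.80 × 0.20 × 1.5) + 1.2816√(0.09 + 0.1875/2)]² / 0.15² = (0.960 + 0.549)² / 0.0225 ≈ 101.3, so 102 vs 204. Then 306/0.8 = 382.5, so 383. Both match. With 400 patients in Arm 1, 80% responders gives 320, or about 107 vs 213; these sizes are used below.

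**2. Full window.** Week 28 to Week 88 is 60 weeks, plus 105 days (15 weeks), giving 75 weeks.

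**3. Follow-up by arm.** The documents give no rate of relapse to sPGA ≥ 3. *Assumption:* the planned 10% and 25% are read as relapse by Week 52 (24 weeks into Part B), with a constant hazard to Week 88.

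- λ = −ln(1 − r)/24, giving 0.00439 (risankizumab) and 0.01199 (placebo) per week.
- S = exp(−60λ) = 0.768 and 0.487, so 23% and 51% are retreated by Week 88.
- Mean follow-up = (1 − S)/λ + 15S = 52.8 + 11.5 = 64.3 weeks, and 42.8 + 7.3 = 50.1 weeks.

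**4. Crude percentages under equal AE hazard h.** P(event) = 1 − {λ/(λ+h) × [1 − exp(−60(λ+h))] + S × exp(−75h)}.

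For h = 0.01 per week (full-window risk 53%):

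- risankizumab: 1 − (0.176 + 0.363) = 46.1%
- placebo: 1 − (0.399 + 0.230) = 37.0%

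Simulation, with no relapse before 4 weeks, gives 46.2 vs 37.1%. For h = 0.005 it gives 27.1 vs 21.4%, and for h = 0.02, 69.1 vs 57.3%.

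**5. How often p ≤ 0.100 is printed.** 6,000 simulated trials per case, 107 vs 213 patients, equal hazards, no psoriasis-worsening events, no dropout:

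| Relapse, risankizumab/placebo | Mean weeks, risankizumab vs placebo | 31% risk | 53% risk | 78% risk |
|---|---|---|---|---|
| Equal follow-up | 75 vs 75 | 8.8% | 9.8% | 8.9% |
| 5%/12.5% by Week 52 | 70 vs 62 | 14.7% | 21.0% | 29.6% |
| 10%/25% by Week 52 | 64 vs 50 | 27.8% | 45.0% | 64.3% |
| 20%/60% by Week 88 (assumed) | 66 vs 45 | 48.0% | 69.9% | 90.5% |

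With unequal follow-up, more than nine in ten of these flags go against risankizumab.

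**6. Where the effect is small.** For full-window risks of 2, 5, 10 and 20%, flags at 10%/25% are 6, 10, 14 and 21%, against 6 to 8% with equal follow-up. At half those relapse rates they are 6, 8, 10 and 12%. With follow-up cut at Week 52, the common events give 9 to 13%, against about 8%. The primary analysis uses a calendar cut-off, so individual follow-up there can run past Week 52.

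**7. *Any AE*.** At 10%/25%, the sign turns to higher on placebo once about 23, 41 or 65% of relapsers (low, middle, high hazard) have worsening psoriasis recorded. If 75% do, the percentages are 42 vs 55, 59 vs 67 and 79 vs 81 (risankizumab vs placebo).

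**8. The existing rate does not repair this.** Suppose its denominator were applied to Part B doses. A patient retreated at Week 32 has a 28-day counting window but contributes 105 days, so the rate is understated by 1 − 28/105 = 73%. At Week 44 it is 112 against 189 days (41%). Read literally for the entire study, a patient retreated at Week 40 with a last dose at Week 56 contributes 56 × 7 + 105 = 497 days.

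**9. Matched first-event rates.** A rate difference on person-time to first event or end of window gives p ≤ 0.100 in 9.3 to 10.4% of trials for the three common-event hazards under all three relapse assumptions.

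**The case against.** The strongest case against is about weight.

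- **The relapse rates are a proxy.** The planned 25% and 10% are loss of sPGA 0/1. Retreatment needs sPGA ≥ 3, and missing Week 52 data generally count as non-response. Retreatment by Week 52 should therefore be lower, which makes the half-rate row at least as plausible. The 20%/60% row has no source in the documents. This stands, so the figures are a range.
- **The consequence is limited.** Serious and rare events are hardly affected, the p-values are nominal and outside the efficacy hierarchy, and no decision hangs on them. This also stands.
- **The plan shows the imbalance.** Part B exposure and retreatment counts are given by arm, and events after retreatment have their own populations. With doses on schedule, SAP 9.0 exposure averages 62.0 vs 48.8 weeks (ratio 0.787), against 64.3 vs 50.2 (0.781) for the counting window. That discloses the imbalance but does not correct the test.
- **Protocol 3.2 confines direct AE comparison with placebo to the first 16 weeks.** In context this explains the crossover of the initial placebo arm. It does not remove the Safety_B_R test in SAP 11.1.
- **The remedy was tested on its own assumptions.** With hazards higher early in Part B but equal between arms, rate-based flags rise to 10 to 17% at the planned and half relapse rates, against 13 to 59% for crude proportions. The rates are better, though not neutral.
- **The table list is a separate document.** A by-arm rate may appear there, and complete tables are promised for Safety_B_R, but the SAP defines none.

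**Conclusion.** The concern holds. Followed as written, the SAP gives a between-arm comparison in Safety_B_R that is biased by length of follow-up, with no rate defined on the same window to set beside it. For common events other than worsening psoriasis, at the final analysis, the chance of a printed p-value with no true difference rises from about 9 to 10% to between 15 and 30% at half the planned loss-of-response rates, and to between 28 and 64% at the planned rates. Almost all of these flags go against risankizumab. The figures assume exponential relapse, constant and equal AE hazards and no dropout; they illustrate size and are not bounds. The effect is minor for rare events and at a Week 52 cut, the direction for *Any AE* is uncertain, and efficacy is untouched. It is worth correcting but does not threaten the trial's main conclusions.

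The conflict between protocol 7.3.4 and the safety tests in SAP 11.1 is a separate documentation point. It applies equally to Safety_A1.

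**What to change.** For Safety_B_R, add by-arm first-event incidence rates per 100 patient-years, with rate differences and 95% confidence intervals, for the AE overview, serious AEs, areas of safety interest and common system organ classes. Make these the main between-arm AE comparison and keep crude percentages as description.

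For each event, count person-time from the first Part B dose to the earliest of first event, first retreatment dose, end of observation, data cut-off or, if not retreated, 105 days after the last Part B dose. Do not reuse the SAP 9.0 exposure: its cap at last injection plus 84 days applies even to retreated patients and departs further from the counting window after a missed or stopped dose. Show the rates with and without psoriasis-worsening terms, and use exact or score intervals where events are few.

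Either drop the AE p-values for Safety_B_R, or list the safety tests in both populations in SAP 14.1 as a change from protocol 7.3.4.

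The cost is SAP wording, one person-time derivation and one extra set of tables. No treatment or data collection changes. The rates assume a roughly constant hazard and that stopping at retreatment is unrelated to the event. The second assumption fails for psoriasis-worsening terms, hence the two versions. Simple Wald intervals are liberal for rare events (p ≤ 0.100 in 12 to 14% of trials at 2% incidence).
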